## **8.7 Vital Signs**

Measurement of vital signs will include an assessment of pulse rate, blood pressure, respiration rate, and temperature. Vital signs will be measured at all study visits, excluding the Follow-up Visit. Blood pressure should be obtained in the seated position, after the subject has rested comfortably for at least 5 minutes. Blood pressure at the Screening Visit should be obtained in both arms and the arm with the highest diastolic value should be used for ongoing monitoring throughout the rest of the study. If an automated assessment is performed, the same machine should be used for the subject throughout the study when possible. Care should be taken to ensure an appropriate cuff size is utilized.

## **8.8 Electrocardiograms**

Electrocardiograms (ECGs) will be performed in triplicate and sent to a central reviewer. Subjects should be lying quietly in a fully supine position for at least 10 minutes prior to each 12-lead ECG. A 12-lead ECG will be performed at the Screening Visit, Study Day 1, Week 2, Week 6, Week 10, Week 12, and the ET Visit, if applicable.

The Investigator will assess ECG data as normal, abnormal not clinically significant, or abnormal clinically significant. Any clinically significant abnormalities should be documented as medical history/adverse event/SAE as applicable. All ECG traces will be kept as source data.

## **8.9 Physical Examinations**

A full physical examination will be performed at the subject's first study visit, either at the Pre-Screening Visit, if applicable, or the Screening Visit, Week 12, and the ET Visit, if applicable.

applicable. A full physical examination includes genitourinary examination per the Investigator's discretion and does not include a rectal examination.

A symptom-directed physical examination will be conducted at the Screening Visit (only for subjects who required a Wash-Out Period and completed the full physical examination at the Pre-Screening Visit), Study Day 1, Week 2, Week 6, Week 10 and the Follow-up Visit (only for subjects who had an abnormal result at Week 12 [or the ET Visit, if applicable] or an ongoing treatment-related adverse event).

Height will be measured at the subject's first study visit, either at the Pre-Screening Visit, if applicable, or the Screening Visit and weight will be measured at all study visits, excluding the Follow-up Visit. BMI will be calculated at the Pre-Screening Visit or Screening Visit, Day 1, Week 10, and Week 12. Waist circumference will be measured at Day 1 and Week 12 [or the ET Visit, if applicable].

#### **8.10 Medical/Surgical History and Demographics**

Medical and surgical history and demographics will be recorded at the Pre-Screening Visit, if applicable, and/or the Screening Visit. Subject eligibility will be evaluated to determine all inclusion and none of the exclusion criteria are met. The Investigator will inquire with the subject at Study Day 1 to determine if there have been any changes in the subject's health affecting eligibility or requiring an update to their medical and surgical history.

#### **8.11 Reserve Samples and Pharmacokinetics (PK)**

Additional blood samples will be collected at all study visits during the Treatment Period and the ET Visit, if applicable, to be available for analysis of exploratory biomarkers associated with lipid metabolism (which may include but will not limited to RLP-C, RLP-TG and RLP-apoB, Lp(a), ox-LDL, and Lp-PLA2), repeat lipid testing, blood drug levels including use in confirming subject compliance (PK analysis), and/or repeat or additional clinical laboratory testing in the event of a safety issue.

Reserve samples will be stored for a minimum of 1 year following study completion and may be stored until the IND is withdrawn or the NDA is approved. If requested, results of tests performed on study samples will be made available to subjects or investigators. Subjects may not withdraw their samples.

The plasma reserve samples collected at Week 2, Week 6, Week 10 and Week 12 [or the ET Visit, if applicable] will be used for the analysis of PK. To facilitate the analysis of PK samples, the time and date of the last dose of study medication and statin if applicable (generic name and strength) prior to the clinic visit will be collected by the subject via a diary. In addition, the time and date of the PK blood sample at the clinic visit will be collected.

#### **8.12 Diary**

All subjects will complete a Sponsor-provided paper diary prior to all study visits that require PK samples. The subject will document the exact date and time of their last dose of study drug and,

if applicable, the last date and time of statin dosing. All diaries should be confirmed to be complete by the Principal Investigator or designee and maintained in the subject's records.

## **9 STATISTICS**

### **9.1 Sample Size**

Approximately 90 subjects (30 subjects per treatment group) will be randomized into 1 of 3 treatment groups: gemcabene 300 mg, gemcabene 600 mg or placebo.

A sample size of 30 randomized subjects in the gemcabene 300 mg group, 30 randomized subjects in the 600 mg group and 30 randomized subjects in the placebo group is expected to provide 80% power to detect a difference of 35% in the percent change in TG from baseline to end of study (EOS) between either of the gemcabene treatment groups and the placebo group. This calculation is based on a 2-sided t-test at the 5% level of significance ( $\alpha = 0.05$ ), a common standard deviation of 43, and a drop-out rate of 15%.

### **9.2 Analysis Populations**

#### **9.2.1 Full Analysis Set**

The Full Analysis Set (FAS) will consist of all randomized subjects who receive at least 1 dose of study drug and have at least 1 post-baseline efficacy assessment. The FAS population will be the primary analysis population. All efficacy analyses will be performed on the FAS.

#### **9.2.2 Per Protocol Set**

The Per Protocol Set (PPS) will include all FAS subjects who complete the 12-week Treatment Period without major protocol deviations. The PPS will be used to assess robustness of the analysis results. Protocol deviations will be reviewed and the PPS will be determined prior to database lock.

#### **9.2.3 Safety Analysis Set**

The Safety Analysis Set (SAS) will include all randomized subjects who receive at least 1 dose of study drug. All safety analyses will be conducted on SAS.

## **9.3 Statistical Methods**

### **9.3.1 Analysis of Efficacy**

#### **9.3.1.1 Primary efficacy analyses**

The primary efficacy endpoint is the percent change in fasting serum TG from baseline to EOS. Baseline will be defined as the average of the (Screening Visits [S1 and S2] or [S2 and S3] occurring up to 28 days prior to Study Day 1) and Study Day 1 [pre-dose]) values. EOS will be defined as the average of Week 10 and Week 12. If either the Week 10 or Week 12 value is missing, then the single value (Week 10 or Week 12) will be used. Completely missing values (both Week 10 and Week 12) will be imputed using last observation carried forward (LOCF), with the last on-treatment value carried forward as the EOS value.

The primary efficacy endpoint will be analyzed using analysis of covariance (ANCOVA) with percent change from baseline to EOS in TG as the dependent variable; treatment and baseline statin (yes or no) as factors; and baseline fasting serum TG as a covariate. The ANCOVA will be performed using the FAS, with subjects included in their randomized treatment group regardless of the treatment they actually received. The least-squares mean (LSM) and standard error (SE) will be provided for each treatment group, along with the placebo-corrected LSM, its 95% confidence interval (CI), and associated p value for both gemcabene groups. A 2-sided test with a significance level of 0.05 will be used for the comparison of the gemcabene 300 mg and 600 mg groups separately to the placebo group. If non-normality is detected, then either the data will be transformed so that it is normally distributed or a nonparametric test will be used.

A confirmatory analysis of the primary efficacy endpoint will be performed using the PPS.

#### 9.3.1.2 Secondary efficacy analyses

Secondary efficacy endpoints include:

- Change and percent change from baseline to Weeks 2, 6, 10 and 12 in fasting serum TG, and change from baseline to EOS in fasting serum TG;
- Change and percent change from baseline to Weeks 2, 6, 10, 12 and EOS in total cholesterol (TC), non-HDL-C, HDL-C, and VLDL-C;
- Change and percent change from baseline to Weeks 10, 12 and EOS in Apo B, ApoA-I, ApoA-II, ApoA-V, ApoC-II, ApoC-III, and ApoE;
- Change and percent change from baseline to Weeks 10, 12 and EOS in LDL-C (ultracentrifugation), LDL-TG, VLDL-TG, HDL-TG;
- Change and percent change from baseline to Week 12 in lipoprotein size and particle number (NMR);
- Change and percent change from baseline to Week 12 in hsCRP, IL-6, SAA, ANGPTL4, adiponectin and fibrinogen; and
- Percent of subjects achieving a TG value <500 mg/dL (5.65 mmol/L) at EOS.

For continuous secondary efficacy endpoints, the same ANCOVA model outlined above for the primary efficacy endpoint will be used, with the respective baseline included as the covariate. Baseline for TC, non-HDL-C, HDL-C, and VLDL-C will be defined as the average of the last two pre-dose values (generally will be the average of Visit S2 and pre-dose Study Day 1/Visit T1). Baseline for fasting apolipoproteins, LDL-C (ultracentrifugation), LDL-TG, VLDL-TG, HDL-TG, hsCRP, IL-6, SAA, adiponectin, fibrinogen, and ANGPTL4 is defined as the value from pre-dose Study Day 1/Visit T1. For the EOS time point, EOS will be defined as the average of Week 10 and Week 12. If either the Week 10 or Week 12 value is missing, then the single value (Week 10 or Week 12) will be used. Completely missing values (both Week 10 and Week 12) will be imputed using LOCF, with the last on-treatment value carried forward as the EOS value. For all other time points, missing values will be imputed using LOCF, with the last on-treatment value carried forward to that time point.

Each ANCOVA will be performed using the FAS, with subjects included in their randomized treatment group regardless of the treatment they actually received. The output from each ANCOVA will include the LSM and SE for each treatment group, along with the placebo-corrected LSM, its 95% confidence interval (CI) and associated p-value for both gemcabene groups. For every continuous endpoint (each parameter, each time point), if non-normality is detected, then either the data will be transformed so that it is normally distributed or a nonparametric test will be used.

The percent of subjects achieving a TG value <500 mg/dL (5.65 mmol/L) will be analyzed using a logistic regression with treatment, baseline statin use (yes or no) and baseline TG value as independent factors. The percent of subjects in each treatment group achieving a TG value <500 mg/dL, and the odds ratios with 95% confidence intervals and p-values will be presented to compare gemcabene 300 mg and gemcabene 600 mg separately with the placebo group.

The secondary efficacy analyses will be repeated using the PPS.

#### 9.3.1.3 Exploratory analysis

The exploratory efficacy endpoints include:

- CI [REDACTED]
- [REDACTED]
- [REDACTED]

For each continuous exploratory endpoint, an ANCOVA will be performed, with the relevant baseline as the covariate. In general, baseline and EOS will be defined as described above in the primary and secondary efficacy analysis sections. Baseline for fasting insulin levels, FPG and HbA1c is defined as the value from pre-dose Study Day 1/Visit T1. The FAS will be used for each analysis, with subjects included in their randomized treatment group regardless of the treatment they actually received. For the analysis of fasting insulin levels, FPG and HbA1c, the FAS that includes only subjects with diabetes at baseline will be used. Where appropriate, relevant subgroups will be used (e.g., within each TG stratum). For each endpoint, the LSM and SE for each treatment group will be provided, along with the placebo-adjusted LSM, 95% CI and p-value for both gemcabene groups.

The percent of diabetic subjects with >5% decrease in dosage of anti-diabetes pharmacologic treatment from baseline to Week 12 will be analyzed using logistic regression with treatment, baseline statin use (yes or no) and baseline TG value as independent factors. The percent of diabetic subjects in each treatment group with > 5% decrease, and the odds ratios with 95%

confidence intervals and p-values will be presented to compare gemcabene 300 mg and 600 mg separately with the placebo group.

The exploratory efficacy analyses will be repeated using the PPS.

### 9.3.2 Analysis of Safety

Safety will be assessed using the SAS. The assessment of safety will include adverse events, clinical laboratory assessments, ECGs, physical examinations, and vital signs. In addition, the safety assessment will be based primarily on the frequency of new or worsening adverse events, laboratory abnormalities, and serious adverse events (SAEs). Other safety data will be summarized as appropriate.

AEs will be coded using the most recent version of the Medical Dictionary for Regulatory Activities (MedDRA). The summarization of AEs will include only treatment-emergent AEs (TEAEs), defined as AEs that begin or worsen after randomization and ingestion of the first dose of study drug. TEAEs and SAEs will be summarized by system organ class (SOC), severity, and relationship to study drug for each treatment group. Deaths, withdrawal from study treatment due to AEs, and withdrawal from the study due to AEs will each be summarized by treatment group.

Safety laboratory data will be summarized by treatment group at baseline, and at each post-baseline time point, if applicable, and change from baseline to End of Treatment (Week 12) or the ET Visit, if applicable. Baseline for safety laboratory data will be defined as the last pre-dose value (pre-dose Study Day 1/Visit T1 or prior). Frequency counts of new or worsening abnormalities will also be provided.

Vital signs data (value and change from baseline, where appropriate) will be summarized by treatment group at baseline and at each post-baseline time point. Baseline for vital signs data will be defined as the last pre-dose value (pre-dose Study Day 1/Visit T1 or prior). Abnormalities in ECGs and in PEs will be summarized.

All safety data will be listed.

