## APPENDIX A: SCHEDULE OF PROCEDURES

	Pre-Screening a	Screening b,f				Treatment Period c				Follow-Up d	ET
		Study Day -28 to -21	Study Day -14 to -7	Study Day-7	Study Day 1 e	Week 2/ Study Day 15±3 days	Week 6/ Study Day 43±3 days	Week 10/ Study Day 71±3 days	Week 12/ Study Day 85 or up to 3 days prior to Study Day 85	Study Day 113	
	Visit Identifier	Visit S1	Visit S2	Visit S3	Visit T1	Visit T2	Visit T3	Visit T4	Visit T5	Visit FU1	
Informed consent	X	X									
Inclusion/exclusion criteria	X	X	X	X	X						
Medical/surgical history and demographics	X	X	X	X	X						
Full physical examination g	X	X							X		X
Symptom-directed physical examination		X h			X	X	X	X		X i	
Vital signs j , height k , and weight	X	X	X	X	X	X	X	X	X		X
Body Mass Index (BMI)	X	X			X			X	X		X
Waist circumference					X				X		X
Urinalysis + NAGL l	X	X			X		X		X	X i	X
Protein:creatinine ratio; albumin:creatinine ratio	X	X			X		X		X	X i	X
Serum/urine pregnancy test m	X	X			X	X	X	X	X	X i	X
Safety chemistry panel, coagulation, and hematology n	X	X	X	X	X	X	X	X	X	X i	X
TSH and serology o	X	X f									
Fasting lipid panel p	X q	X	X	X	X	X	X	X	X	X	X
Fasting apolipoproteins r					X			X	X	X	X
LDL-C ultracentrifugation (LDL-C, LDL-TG, VLDL-TG)					X			X	X	X	X
Cl ██████████					X				X		X
HbA1c	X	X			X				X		X
Cystatin-C, ANGPTL4, adiponectin					X				X		X

hsCRP, SAA, IL-6, and fibrinogen					X			X	X		X
Lipoprotein size and particle number					X				X		X
Randomization					X						
Study drug administration s					X	X	X	X			
Dispense study drug and instructions					X	X	X	X			
Compliance check						X	X	X	X		X
Distribute drug diary					X	X	X	X			
Dietary assessment (self-reported) t	X	X	X	X	X	X	X	X			
12-lead ECG u		X			X	X	X	X	X		X
Initiate wash-out	X										
Adverse events	X v	X v	X	X	X	X	X	X	X	X	X
Concomitant medications	X	X f	X	X	X	X	X	X	X	X	X
Reserve serum samples w					X	X	X	X	X		X
Reserve plasma PK samples x					X	X	X	X	X		X
Collect drug diary						X	X	X	X		X
Reserve genotyping sample					X						

Footnotes appear on the following page

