Change from baseline (CFBL) for a given parameter (eg, y) for a given subject will be calculated as  $y_t - y_b$ , where  $y_t$  is a given subject's value  $t$  weeks post-baseline and  $y_b$  is a given subject's value at baseline. CFBL will be computed for subjects with a baseline value and a post-baseline value. In order to be included in a CFBL analysis for a given parameter, a subject must have a baseline value. If a subject does not have a baseline value, they will be excluded from the CFBL analysis. Percent CFBL for a given subject and parameter will be computed as  $\left(\frac{y_t - y_b}{y_b}\right) * 100$  (ie, CFBL divided by the baseline value and multiplied by 100). Percent CFBL will only be computed for subjects with a CFBL value. Additionally, subjects with a value of 0 at baseline will not have percent CFBL computed.

For efficacy parameters, end of treatment is defined as the last non-missing post-baseline value collected while on treatment or within 2 days of treatment (last dose) for a given subject. For safety parameters, end of treatment is defined as the last non-missing post-baseline value collected while on treatment or within 5 days of last dose.

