## **12.2 Clinical Laboratory Assessments**

The laboratory parameters below will be summarized at baseline and at each post-baseline time point by treatment group, using the SAS. CFBL to each time point including end of treatment for each of the following laboratory parameters will also be summarized by treatment group.

Chemistry: alanine aminotransferase (ALT), albumin, alkaline phosphatase (ALP), aspartate aminotransferase (AST), bicarbonate, blood urea nitrogen (BUN), calcium, chloride, creatine kinase (CK), creatinine, gamma-glutamyl transferase (GGT), glucose, lactate dehydrogenase (LDH), phosphorus, potassium, sodium, (total) bilirubin, (total) protein, estimated glomerular filtration rate (GFR), cystatin-C

Hematology: hemoglobin, hematocrit, leukocytes, basophils, eosinophils, lymphocytes, monocytes, neutrophils, platelets, red blood cell count, mean corpuscular hemoglobin concentration, mean corpuscular hemoglobin, mean corpuscular volume

Coagulation: prothrombin time, activated partial thromboplastin time, international normalized ratio

Urinalysis: pH, specific gravity, NGAL, creatinine, protein, protein/creatinine ratio, albumin, albumin/creatinine ratio

If, for a given subject at a given visit, the absolute count of neutrophils are not provided but segmented and band neutrophils are, segmented and band neutrophils are summed to determine the absolute count of neutrophils. If only segmented neutrophils are provided, they are used as the absolute count of neutrophils. Similarly, if neutrophils/leukocytes are not provided at a given visit but neutrophils (segmented)/leukocytes are, neutrophils (segmented)/leukocytes are used as neutrophils/leukocytes.

If a laboratory value is lower or higher than the detection limit (eg, <XX.X), the value will not contribute to summary statistics but will be included in the listings.

Out-of-range values will be assessed using shift tables. Laboratory values will be identified as low, normal, or high based on the normal ranges provided by the central laboratory. Shift tables for each parameter will display, for each treatment group, the number of subjects with low, normal, and high values at baseline and end of treatment. Percentages will be based on the number of subjects in each category at baseline.

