Potentially clinically significant out-of-range values will also be summarized for safety laboratory parameters. The potentially clinically significant (PCS) values are found in Table 3. The number and percent of subjects meeting the criteria below for single occurrences and consecutive (multiple) occurrences will be summarized by treatment group. Summaries will consider any time post-baseline. The denominator for a given percentage will be the number of subjects who are eligible for each criterion (eg, had a post-baseline assessment or had consecutive post-baseline assessments for the corresponding parameter). Additionally, for subjects with post-baseline chemistry laboratory values meeting the PCS criteria at consecutive visits, all laboratory values (including urinalysis parameters) will be provided in a listing.

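### The SAP's shift tables use only the last on-treatment value, so for 34 parameters a resolved abnormality enters no laboratory-abnormality count, although the protocol promises counts of new or worsening abnormalities

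*Protocol*

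**What the plan says.** Protocol 9.3.2 (repeated in the synopsis) states that "the safety assessment will be based primarily on the frequency of new or worsening adverse events, laboratory abnormalities, and serious adverse events". For laboratory data it then promises: "Frequency counts of new or worsening abnormalities will also be provided". The same paragraph ties the change-from-baseline summary to Week 12 or the early termination visit, but attaches no time point to the counts.

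Protocol Appendix A schedules "Safety chemistry panel, coagulation, and hematology" at every treatment visit, so each blood parameter in those panels has results at Weeks 2, 6, 10 and 12. Urine is collected at Week 6 and Week 12 (Protocol 8.6).

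SAP 12.2 says that out-of-range values are assessed by shift tables showing "the number of subjects with low, normal, and high values at baseline and end of treatment". For safety parameters, SAP 9.2 specifies that "end of treatment is defined as the last non-missing post-baseline value collected while on treatment or within 5 days of last dose". That is one value per subject. SAP 12.2 also has a PCS table, of which it says: "Summaries will consider any time post-baseline". Its criteria are limited to the parameters in Table 3.

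SAP 4.3, which lists changes from the protocol's analyses, has no entry on laboratory abnormalities.

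**The concern.** A subject who is normal at baseline, abnormal at Week 6 and normal again at the last value appears in the shift table as normal-to-normal. Unless the parameter has a PCS row and the value crosses its threshold, no laboratory table records that the abnormality occurred. By-visit means, medians, minima and maxima do not count subjects, and listings give no frequency by arm.

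This matters because safety is a secondary objective and the protocol names the frequency of laboratory abnormalities as a basis separate from adverse events. Some parameters without a PCS row are ones the protocol itself relies on. Total bilirubin, INR and eosinophilia appear in the hepatic discontinuation criteria of Appendix E. Protocol 8.1.4.2 uses NGAL to find subjects whose creatinine and BUN look unremarkable but who may need closer renal follow-up. With about 30 subjects per arm, losing a few cases from a count can hide a difference between arms.

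**Working it through.** The documents state no figure for how many parameters are affected, so there is none to reproduce. The count is taken from the SAP's own lists.

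**Step 1. Parameters summarized (SAP 12.2).** Chemistry 20, hematology 13, coagulation 3, urinalysis 8: 20 + 13 + 3 + 8 = 44.

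**Step 2. Parameters with an any-time count (SAP Table 3).** ALT, AST, BUN, creatine kinase, creatinine, estimated GFR, hemoglobin, urine protein/creatinine ratio and urine albumin/creatinine ratio: 9. Without one: 44 − 9 = 35.

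**Step 3. Remove parameters with no scheduled sample before Week 12.** Cystatin-C is measured only at baseline and Week 12 or early termination (Protocol 8.1.4.2 and 8.6). 35 − 1 = 34.

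| Panel | Summarized | With PCS row | No interim sample | Affected |
|---|---|---|---|---|
| Chemistry | 20 | 6 | 1 | 13 |
| Hematology | 13 | 1 | 0 | 12 |
| Coagulation | 3 | 0 | 0 | 3 |
| Urinalysis | 8 | 2 | 0 | 6 |
| Total | 44 | 9 | 1 | 34 |

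The affected blood parameters number 13 + 12 + 3 = 28; they include neutrophils, platelets, eosinophils, potassium, bilirubin and INR. For a subject who completes treatment, three of the four scheduled results for each enter no laboratory-abnormality count. The 6 urine parameters (pH, specific gravity, NGAL, creatinine, protein, albumin) are affected at Week 6 only.

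**Step 4. What the PCS rows leave out.** For the 9 covered parameters, transient out-of-range values below the threshold are also uncounted, for example ALT between 1 and 2 × ULN. The criteria set as multiples of ULN do not require a normal baseline, so they do not isolate new abnormalities.

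**Step 5. Illustration of how much a last-value rule can miss.** Assume four scheduled on-treatment results, a normal baseline, and timing uniform over the possible positions. These are assumptions, not figures from the documents.

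- Episode at one visit: the last value shows it in 1 of 4 positions, 25%.
- Episode at two consecutive visits: three possible pairs, one of which includes Week 12, so 1/3 = 33%.
- If 6 of 30 subjects in an arm had a one-visit episode, the number shown is Binomial(6, 0.25). The mean is 6 × 0.25 = 1.5. P(0 or 1) = 0.75^6 + 6 × 0.25 × 0.75^5 = 0.178 + 0.356 = 0.534.

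**The case against.** Several points on the other side are sound.

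- **Adverse event tables.** A reader might infer that a resolved abnormality is counted nowhere. The documents do not support that. Protocol 8.1 treats clinically significant laboratory abnormalities as adverse events from the first dose, and SAP 12.1 tabulates treatment-emergent events whenever they start on treatment. This is only partial cover: it depends on investigator judgement, and Protocol 8.1 does not require a result unverified by repeat testing to be reported.
- **Drug interruption.** A reader might also infer that the last-value rule hides the very subjects whose drug was interrupted for an abnormal result. This fails. The laboratory triggers for temporary interruption in Appendix E are creatine kinase and ALT. Both have any-time PCS rows at lower thresholds, and SAP 12.1 counts interruptions due to adverse events.
- **The protocol sentence sets no time point.** Shift tables plus PCS counts are frequency counts of a kind, so undeclared departure is a reading rather than a literal contradiction. That is fair. But a baseline-to-last-value table does not count abnormalities that were new on treatment and then resolved, and nothing in the sentence excludes them.
- **PCS targets the expected risks.** Table 3 covers the liver, muscle, renal and hemoglobin concerns in Protocol 8.1.4. The one laboratory time course in Protocol 1.4, creatinine and BUN rising within 2 to 4 weeks, concerns covered parameters and is described as reversing after the drug is stopped, not while on it. The documents therefore do not show that transient abnormalities are expected in the uncovered parameters.
- **Overlap and visibility.** Some uncovered items overlap covered ones (hematocrit with hemoglobin, urine protein with its ratio). Extreme values would show in by-visit minima and maxima, and everything is listed. None of this gives a number of subjects per arm.

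**Conclusion.** The point holds in a limited form. For 34 of the 43 summarized parameters that have a scheduled on-treatment sample before Week 12, the SAP as written leaves an abnormality that resolves before the last value out of every laboratory-abnormality count. If it is not reported as an adverse event, it shows only in listings and by-visit descriptive statistics. The protocol's promise is broader than that, and the SAP does not say that it has been narrowed.

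The count of 34 rests only on the SAP's parameter lists and the protocol's sampling schedule. The 25% and 33% capture figures rest on assumed uniform timing and show direction and scale only. The primary endpoint is unaffected. The SAP should be corrected because the gap lies in an output that the protocol calls a main basis of the safety assessment and the data are already being collected.

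**What to change.** In SAP 12.2, add for every summarized parameter a shift from the baseline category to the worst post-baseline on-treatment category, taken separately for the lowest and the highest value. Use all scheduled and unscheduled results within the SAP's existing 5-day safety window, so that the one-result-per-visit-window rule of SAP 9.8 does not drop any. Report by arm the number and percent of subjects with a new or worsened low or high value. State what counts as worsened for a subject already out of range at baseline, since low, normal and high categories alone cannot show it. Keep the end-of-treatment shift as a second table.

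The cost is SAP wording and one more standard table per laboratory panel, with no new data. The drawback is that more chance abnormalities will be displayed, in all arms. If the sponsor prefers to keep the narrower tables, SAP 4.3 should at least declare the change; that would make the plan transparent but would not supply the missing counts.
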